#### 7.5.2 CONCOMITANT MEDICATIONS

Concomitant and prior medications taken within 30 days prior to Screening Visit will be summarized by ATC Level 3.

#### 7.6 EFFICACY

Efficacy will be assessed using the response based upon overall survival, time to progression, RECIST, and hepatitis viral load. Liver chemistry tests and viral load will be presented as exploratory efficacy variables, as will AFP and WBC A3AR expression. Summaries of efficacy variables by visit will be presented using visits through end of Cycle 11. Analyses of time to event (OS, TTP, and PFS) and Best Overall Response will not be restricted to visits through Cycle 11. All efficacy data will be listed. Binary response variables will not be analyzed using SAS PROC FREQ, which uses equal variances for the differences, as opposed to the unequal variances given below.

## 7.6.1 OVERALL SURVIVAL (OS)

Overall survival (OS) is the time from Baseline to death due to any cause. OS will be summarized in months, which will be obtained by dividing OS in days by 30 days/month. Subjects who are alive at last contact will be considered censored at the date of last contact. Summary statistics (25th percentile, median, and 75th percentile) will be determined using the Kaplan-Meier (KM) estimate of the survival function. These summary statistics will be listed to one decimal place, rounded down such as the SAS FLOOR function. The KM curve for OS will be presented. The value of the KM curve for OS at the median duration of therapy (Section 7.5.1) will be presented. The between-treatment comparison will be performed using the logrank test as the primary analysis. Between-treatment comparisons with respect to OS will be also performed using the proportional hazards model with AFP at Baseline and A3AR level at Baseline as covariates individually as secondary analyses, including the hazard ratio and the 95% confidence interval for the hazard ratios for both treatment and the covariate. Additional details are given in Section 9.

## 7.6.2 TIME TO PROGRESSION (TTP)

Time to Progression (TTP) is the time from Baseline to the first Overall Response of Progressive Disease (PD), computed as in Section 6.1.1. TTP will be summarized in months, which will be obtained by dividing TTP in days by 30 days/month. Subjects who do not have an Overall Response of PD by the time of last contact will be considered censored at the date of last contact; subjects who died without experiencing PD will be censored at the day of death. Summary statistics (25th percentile, median, and 75th percentile) will be determined using the KM estimate of the survival function for TTP. These summary statistics will be listed to one decimal place, rounded down such as the SAS FLOOR function. The KM curve for TTP will be presented. The value of the KM curve for TTP at the median duration of therapy (Section 7.5.1) will be presented. The between-treatment comparison will be performed using the logrank test. Additional details are given in Section 9.

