10.2 Time to Event

The time to event assessments include OS, TTP, and PFS. Overall Survival (OS) is the number of days from Day 1 of Cycle 1 to the day of death+1, where a death can be due to any cause. Subjects who discontinue will be followed indefinitely to obtain survival status. Time to Progression (TTP) is the number of days from Day 1 of Cycle 1 to the day of PD+1. Progression-Free Survival is the number of days from Day 1 of Cycle 1 to the day of death or PD+1.

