11.2 Duration of Follow-Up

Any significant clinical adverse event, whether observed by the Investigator or experienced by the subject, will be reported beginning with the Cycle 1 Day 1 (Baseline) Visit. Final safety evaluations will be performed at the 28-day Follow-Up Visit (28 ± 3 days post End of Dosing)/OL Follow-Up Visit (28 ± 3 days post OL End of Dosing). If the subject begins an alternative treatment, then the Follow-Up visit will be performed as soon as possible. Every effort will be made to obtain and record survival information for each subject, who will be followed indefinitely for survival with, for example, monthly telephone calls.

If an observed toxicity thought to be at least possibly related to study drug has not resolved by the 28-Day Follow-Up Visit/OL Follow-Up Visit, the subject will continue to be followed until the event has resolved or stabilized.

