#### 6. STUDY ENDPOINTS

Baseline typically refers to Day 1 of Cycle 1 and Screening refers to the Pre-Study Visit. For some variables, Baseline is Cycle 1 Day 1 unless the assessment was performed at Screening which was  $\leq 3$  days prior to Cycle 1 Day 1, in which case the assessment was not to be repeated (footnotes 'a' and 'c' of Table 1-1). In the protocol and footnotes above, some assessments are given as performed at Day 28 or 29 of a cycle; consistent with the table above and the CRFs, these assessments are described below as being performed at Day 1 of the following cycle.

Tumor assessments performed at the End of Study/ End of Dosing (EOS) Visit, the Follow-up Visit, and Unscheduled Visits will be assigned to the next cycle for calculation of summary statistics.

The subjects who are still on blinded treatment when Amendment 5 is approved will be switched to open-label treatment at their next scheduled visit. The first day of open-label study drug dosing will be considered Day 1 (OL) of the trial. During this visit, the OL Cycle 1 Day 1 for OL procedures will be performed ( $\underline{\text{Table 1-2}}$ ). During the OL period, clinic visits will take place within  $\pm$  2 working days of the scheduled day; during these visits, assessments will be performed prior to administration of the study drug dose for that day.

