#### 6.1 EFFICACY ASSESSMENTS

Tumor response will be assessed at the Pre-Study Visit, Day 1 of odd-numbered cycles, and at the follow-up visit using Response Evaluation Criteria In Solid Tumors (RECIST v1.1) from Eisenhauer et al. (2009), presented in Appendix A of the protocol, and further described below in Appendix B. In general, target lesions will be assessed as Complete Response (CR), Partial Response (PR), Stable Disease (SD), or Progressive Disease (PD) and non-target lesions will be assessed as Complete Response (CR), Incomplete Response/Stable Disease (SD), or Progressive Disease (PD). Tumor responses from target lesions and from non-target lesions will be used to determine Overall Response as described in Appendix B. If the Overall Response is CR or PR, tumor assessments are to be repeated within 4 weeks. Overall Response will be tabulated by cycle and treatment; the responses for target lesions and non-target lesions will be included in listings, but will not be tabulated. If Overall Response of PD is observed at any time, the patient will not automatically be discontinued. Further imaging or target lesion measurements will not be required and all other trial visits and procedures will continue.

If assessments are made after the Overall Response of PD is recorded, then the Overall Response at all subsequent cycles will be PD and will be included at every cycle for which the Overall Response is recorded through Cycle 11 (see Section 7.2).

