# Listing 16.2.5.1

#### Time to Event

Site/		Date of	Progressive		Date of	Date of First	Date of Last	OS	TTP	PFS
Subject	Treatment	First Dose	Disease?	Death?	Death	Progression	Contact	(months)	(months)	(months)
xxx/xxxxx	XXXX	DD/MM/YY	Yes	Yes	DD/MM/YY	DD/MM/YY	DD/MM/YY	XX.X	XX.X	XX.X
xxx/xxxxx	XXXX	DD/MM/YY	Yes	No		DD/MM/YY	DD/MM/YY	XX.X *	XX.X	XX.X
xxx/xxxxx	XXXX	DD/MM/YY	No	No			DD/MM/YY	XX.X *	XX.X *	XX.X *
xxx/xxxxx	XXXX	DD/MM/YY	No	Yes	DD/MM/YY		DD/MM/YY	XX.X	XX.X *	XX.X

OS= Overall Survival (Time to Death due to any cause); TTP=Time to Progression; PFS= Progression-Free Survival (Time to Progression or Death) \* indicates censored value.

Programming Notes: If an event did not occur, leave the date of the event blank. Date of Last Contact is the last date known to be alive in next listing.

Add \* for censored values, defined as follows.

OS is time to death due to any cause and is censored at date of last contact if death is not reported.

TTP is time to progression and is censored at date of last contact (including death) if progression is not reported.

PFS is time to progression or death and is censored at date of last contact if neither progression nor death is reported.

Listing 16.2.5.2 Survival Follow-up Contact Dates

Site/ Subject	Treatment	Follow-up Date	Is the Subject Alive?	Last date known to be alive	If not alive, date of death
xxx/xxxxx	XXXX	DD/MM/YY	XX	DD/MM/YY	DD/MM/YY
		DD/MM/YY	XX	DD/MM/YY	DD/MM/YY
		DD/MM/YY	XX	DD/MM/YY	DD/MM/YY
xxx/xxxxx	XXXX	DD/MM/YY	XX	DD/MM/YY	DD/MM/YY
		DD/MM/YY	XX	DD/MM/YY	DD/MM/YY
		DD/MM/YY	XX	DD/MM/YY	DD/MM/YY

Includes all subjects who discontinue from dosing.

Programming Notes: Continue for all follow-up dates.

The CRF Page is to be completed for all subjects who discontinue from dosing.

Listing 16.2.6.1.1
Tumor Evaluations: Target Lesions

Site/				Site		Assessment	Method	Longest
Subject	Treatment	Cycle	Lesion#	Code (1)	Description	Date	Code (2)	Diameter (LD)
xxx/xxxx	XXXXX	Screening	XX	XX	XXXXXX	DD/MM/YY	XXX	XXX
		_	XX	XX	XXXXXX	DD/MM/YY	XXX	XXX
			XX	XX	XXXXXX	DD/MM/YY	XXX	XXX
			XX	XX	XXXXXX	DD/MM/YY	XXX	XXX
		Cycle 3	XX	XX	XXXXXX	DD/MM/YY	XXX	XXX
		XX	XX	XXXXXX	DD/MM/YY	XXX	XXX	
			XX	XX	XXXXXX	DD/MM/YY	XXX	XXX
			XX	XX	XXXXXX	DD/MM/YY	XXX	XXX
		Cycle 5	XX	XX	XXXXXX	DD/MM/YY	XXX	XXX
			XX	XX	XXXXXX	DD/MM/YY	XXX	XXX
			XX	XX	XXXXXX	DD/MM/YY	XXX	XXX
			XX	XX	XXXXXX	DD/MM/YY	XXX	XXX

 Site Codes:

Programming Notes: Continue for all odd-numbered cycles.

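### TTP is censored at last contact or death instead of the last scan, which can raise but never lower each arm's Kaplan-Meier TTP curve; a last-scan sensitivity analysis should be shown beside it

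*SAP*

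**What the plan says.** Protocol 10.2 defines the endpoint ("Time to Progression (TTP) is the number of days from Day 1 of Cycle 1 to the day of PD+1") but gives no censoring rule. SAP 7.6.2 supplies one: subjects that "do not have an Overall Response of PD by the time of last contact will be considered censored at the date of last contact", while for deaths it adds that "subjects who died without experiencing PD will be censored at the day of death". The programming note to mock Listing 16.2.5.1 repeats it ("TTP is time to progression and is censored at date of last contact (including death) if progression is not reported") and fixes the meaning of last contact: "Date of Last Contact is the last date known to be alive in next listing". That next listing, 16.2.5.2, is the survival follow-up log for subjects who discontinue dosing.

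On imaging, Table 1-1 and Protocol 9.3.4 to 9.3.7 schedule scans at the end of even-numbered cycles and at the end-of-dosing (EOS) visit, and none at the 28-day follow-up visit. SAP 6.1 differs: "Tumor response will be assessed at the Pre-Study Visit, Day 1 of odd-numbered cycles, and at the follow-up visit". SAP Section 6 also makes use of off-schedule scans, since those at the EOS visit, "the Follow-up Visit, and Unscheduled Visits will be assigned to the next cycle for calculation of summary statistics". Neither document schedules imaging after the follow-up visit. Survival contact does continue; Protocol 11.2 describes subjects "who will be followed indefinitely for survival with, for example, monthly telephone calls".

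**The concern.** A telephone call can establish that a subject is alive; it cannot establish that the tumour has not progressed. Dosing continues past PD (Protocol 9.2.12), and Protocol 7.4 lists reasons to stop that can come before PD: toxicity, withdrawn consent, investigator discretion and intercurrent illness. A subject who stops for one of these reasons stays in the TTP risk set until last contact or death, with no scheduled way for PD to be found.

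This sits badly with the plan's own standard. RECIST 4.4.2, in Appendix A, treats a time point without imaging as not evaluable, and 4.4.4 expects the analysis plan to say how missing assessments are handled. SAP Section 8 has no rule for tumour assessments.

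TTP is a named secondary endpoint with its own block in Table 14.2.1 and its own figure. At stake is whether a long or unreached upper quartile reflects disease control or an absence of scans.

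**Working it through.** **The plan's own figure.** None is stated for TTP. The one design figure used below is the cut at 75 deaths, which reproduces for OS: (1.960 + 0.842)² / [(1/3)(2/3)(ln 0.5)²] = 7.85 / 0.1068 = 73.5, so 74 events; 75 events give 80.8% power.

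**Direction.** The Kaplan-Meier estimate is S(t) = Π(1 − d/n) over PD times. Both rules use the same PD dates, so each d is the same. Later censoring adds k ≥ 0 subjects to each risk set, and 1 − d/(n + k) ≥ 1 − d/n. Every factor, and so the curve, its quartiles and its value at any time, is equal or higher. In 10,000 random data sets there was no reversal.

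**Size: inputs.** From the documents: 52 v 26 subjects, accrual over 78 weeks, scans every 8 weeks plus EOS, cut at 75 deaths. Assumed: exponential times, no treatment effect, progression median 12 weeks, OS median 26 weeks. That OS value lies between two figures in the protocol: about 2 months (9 weeks) in Section 4.5.2 and 9.5 months (41 weeks) for Child-Pugh B in Section 4.2.2.

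**Stopping independent of death.** Each cell is SAP rule / last-scan rule; the arms are pooled for the Kaplan-Meier estimate.

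| Median time to stopping | KM at median duration of therapy | KM median (wk) | 75th percentile (wk) |
|---|---|---|---|
| 13 wk | 0.76 / 0.68 | 32 / 16 | not reached / 24 |
| 26 wk | 0.64 / 0.57 | 16 / 16 | not reached / 24 |
| 39 wk | 0.56 / 0.50 | 16 / 16 | 56 / 24 |
| 60 wk | 0.48 / 0.43 | 16 / 16 | 40 / 24 |
| 100 wk | 0.41 / 0.38 | 16 / 16 | 32 / 24 |
| none before death | 0.29 / 0.29 | 16 / 16 | equal |

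The 25th percentile is 8 / 8 weeks throughout. Quartiles fall mostly on an 8-week grid, so a one-step difference is within simulation noise. With an OS median of 41 weeks the gap at the median duration of therapy reaches 11 points; with 9 weeks it is at most 2 (stopping medians of 13 weeks or more).

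**Stopping tied to death.** If subjects stop a median 2 or 4 weeks before death, the 75th percentile is 24 / 24 or 32 / 24 weeks, the KM median is 16 / 16, and KM at 26 weeks is 0.24 / 0.22 or 0.28 / 0.22. At 8 weeks before death KM at 26 weeks is 0.34 / 0.22, the 75th percentile still lies within 24 to 32 weeks, and the gap at the median duration of therapy is at its largest for this OS median, about 9 points.

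**What drives the size.** With stopping 2 to 4 weeks before death, 28 to 31 of 78 subjects stop without PD, yet little changes. With independent stopping at 39 weeks only about 14 do, but each adds about 36 unscanned weeks (14 × 36 ≈ 500 subject-weeks). Both the number of stoppers and their later survival matter.

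**If the SAP 6.1 follow-up scan is done.** KM at 26 weeks becomes 0.43 / 0.19 for 13-week stopping (0.52 / 0.19 without that scan) and 0.32 / 0.22 for 39-week stopping (0.36 / 0.23 without). The gap narrows but remains.

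**Between arms.** False-benefit rate against a nominal 2.5%, SAP rule v last-scan: equal 13-week stopping 2.9% v 2.4%, with a standard error of √(0.025 × 0.975 / 1500) ≈ 0.4 points; CF102 26 and placebo 39 weeks 4.9% v 2.0%; CF102 39 and placebo 26 weeks 1.4% v 3.8%.

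**The case against.** The strongest reply concerns size. No stopping pattern is documented. Treatment runs until drug-related intolerability and PD does not end it, so stopping may well cluster near death, where the two rules almost agree. The only guide in the documents points the same way: Protocol 4.2.2 reports 12 subjects treated for at least 6 months in a trial of 19. That is 63% (exact 95% interval 38% to 84%), against an expected 26-week survival of 0.5^(26/41) = 64% at an OS median of 41 weeks, which leaves almost no room for stopping before death. That trial was open-label and mixed Child-Pugh A and B, and its lower limit would allow a stopping median near 35 weeks, so this tempers the size but does not settle it.

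The comparator is not the truth either. With 26-week stopping, the true value at the median duration of therapy is about 0.47; last-scan censoring gives 0.57 and the SAP rule 0.64. Most of that error comes from finding PD only at 8-weekly scans, which a change of censoring date leaves in place. Last-scan censoring also assumes that stopping is unrelated to progression.

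Both points stand. They limit the size and rule out replacing the existing rule. They do not touch the direction, or the fact that unscanned time is counted as progression-free.

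**Conclusion.** The point holds as a reporting weakness in a secondary endpoint. Compared with last-scan censoring on the same PD dates, the SAP rule can raise each arm's TTP curve and cannot lower it. Under a progression median of 12 weeks and an OS median of 26 weeks, the exposed results are the 75th percentile and the tail of the curve, and to a lesser degree the value at the median duration of therapy. The lower quartile is not exposed, and the median moves only if many subjects stop early and then live on unscanned.

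Three stronger readings are tempting and not supported. A reader might infer that TTP is grossly inflated: with 8-week stopping, KM at 26 weeks is 0.61 v 0.17. But the SAP does not tabulate that time point, and nothing in the documents supports such early stopping followed by long survival. A reader might infer that the rule favours CF102: with equal stopping the error rate is close to nominal, and with unequal stopping either rule can be off in either direction. A reader might extend the point to other endpoints: OS is unaffected, and PFS counts deaths as events, so with 75 of 78 subjects dead it changes negligibly.

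**What to change.** In SAP 7.6.2 and the Listing 16.2.5.1 programming note, add a sensitivity TTP analysis (Kaplan-Meier summaries and log-rank) in which subjects without PD, including those who die without PD, are censored at their last evaluable tumour assessment, scheduled or unscheduled, or at Cycle 1 Day 1 if they have none. Show it beside the existing rule in Table 14.2.1.

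Report by arm the number who stopped dosing without PD and the time from last scan to last contact or death, so that readers can see whether the difference matters. Label the analysis as a late addition in Section 9 or the study report; the SAP already records analyses decided after unblinding. Reconcile SAP 6.1 with Table 1-1 on whether a scan is done at the follow-up visit. OS and PFS need no change.

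The cost is a little programming, since assessment dates are already in Listings 16.2.6.1.1 and 16.2.6.2, plus a late addition to a secondary endpoint and TTP estimates that may look less favourable.

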# 7.6.3 PROGRESSION-FREE SURVIVAL (PFS)

Progression-free Survival (PFS) is the time from Baseline to the first Overall Response of Progressive Disease (PD) or death due to any cause if the subject dies without experiencing PD, computed as in Section 6.1.1. PFS will be summarized in months, which will be obtained by dividing PFS in days by 30 days/month. Subjects who are alive without experiencing an Overall Response of PD at the time of last contact will be considered censored at the date of last contact. Summary statistics (25th percentile, median, and 75th percentile) will be determined using the KM estimate of the survival function for PFS. These summary statistics will be listed to one decimal place, rounded down such as the SAS FLOOR function. The KM curve for PFS will be presented. The value of the KM curve for PFS at the median duration of therapy (Section 7.5.1) will be presented. The between-treatment comparison will be performed using the logrank test. Additional details are given in Section 9.

#### 7.6.4 TUMOR RESPONSE

The Objective Response Rate (ORR) is the percentage of subjects who achieved either CR or PR. ORR will be summarized using counts and percentages for the ITT Population by treatment and cycle. The between-treatment comparison will be performed using the normal approximation to the binomial distribution (NAB) with unequal variances, as follows.

For each cycle, let  $p_{CF}$  and  $p_0$  denote the proportions of subjects who experienced CR or PR based on  $n_{CF}$  and  $n_0$  subjects for CF102 and Placebo, respectively, and let

 $Z=(p_{CF}-p_0)/(p_{CF}(1-p_{CF})/n_{CF}+p_0(1-p_0)/n_0)^{1/2}$ .

Then the corresponding p-value is p=2\*(1-PROBNORM(ABS(Z))).

The Disease Control Rate (DCR) is the percentage of subjects who achieved either CR, PR, or SD. DCR will be summarized using counts and percentages for the ITT Population by treatment and cycle. The between-treatment comparison will be performed using the (NAB), similar to that for ORR.

For each subject, the Best Overall Response during the duration of the study will be determined and will be summarized using counts and percentages for the ITT Population by treatment. The between-treatment comparison will be performed using the NAB, for both the percentage of subjects who achieved either CR or PR (similar to ORR) and the percentage of subjects who achieved either CR, PR, or SD (similar to DCR).

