4.2.2 Phase 1/2 Trial in Subjects with HCC (Study CF102-102HCC)

An open-label trial was conducted in 19 subjects with advanced unresectable HCC to evaluate the safety and PK profile of CF102 given orally (1, 5, and 25 mg BID) in 28-day cycles (Stemmer, 2013). Evaluation of the antitumor effects and the utilization of A₃AR as a biological predictive marker of response to CF102 were secondary objectives.

CF102 demonstrated good oral bioavailability and linear PK behavior in subjects with Child-Pugh A and B hepatic dysfunction. The best response by RECIST criteria was SD in 5/17 subjects (29.4%). Median overall survival (OS) was 8.2 months for all subjects, 8.3 months for subjects with no prior sorafenib use, and 7.2 months for subjects with prior sorafenib and for Child-Pugh class A hepatic dysfunction subjects. Median OS in Child-Pugh class B hepatic dysfunction subjects was 9.5 months.

These results are encouraging in light of the fact that 63% of the subject population had disease progression on sorafenib and that, for these subjects, CF102 treatment was second-line therapy.

The most common adverse events (all causalities combined) were decreased appetite (52.6%); fatigue (42.1%); abdominal pain, constipation, and diarrhea (31.6% each); ascites and pyrexia (26.3% each); and nausea, asthenia, back pain, and pain in extremity (21.1% each). CF102-related AEs included fatigue (26.3%), asthenia and decreased appetite (21.1% each), and pyrexia and constipation (15.8% each). Grade 3 drug-related AEs included: cerebral hemorrhage, headache, hyponatraemia, fatigue, asthenia, and back pain. One death (5.3%) due to cerebral hemorrhage was judged possibly related to CF102 by the Investigator. SAEs with fatal outcomes in 5 subjects were judged as not related to CF102.

CF102 had no adverse effect on routine measures of liver function over a 6-month period in 12 subjects treated for at least that duration. No dose-limiting toxicities were observed during the trial and the MTD was not reached.

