6.3 Number of Subjects

Approximately 78 subjects will be enrolled and randomized in a 2:1 ratio to receive treatment with either CF102 or matching placebo.

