12.4.2 Efficacy Data

All efficacy analyses will be performed for the ITT Population. Tumor response will be analyzed for the PP Population, with the analyses for the ITT Population being primary.

Time to event variables will be summarized using the number observed, number censored, median, and 25th and 75th percentiles from Kaplan-Meier curves. Data will be summarized using descriptive statistics (number of subjects (n), mean, median, standard deviation, minimum, and maximum) for continuous variables. Categorical variables will be summarized using frequencies and percentages.

Between-treatment comparisons with respect to OS, TTP, and PFS will be performed using logrank tests, with Cox's proportional hazards regression model used for supportive analyses to assess the impact of covariates. Tumor lesion measurements and changes from baseline will be summarized by cycle and treatment. Objective response rates and DC rates will be presented and between-treatment comparisons will be performed using the normal approximation to the binomial distribution by treatment for each even-numbered cycle. Between-treatment comparisons with respect to AFP will be performed using Analysis of Covariance (ANCOVA) with the value at baseline value used as a covariate and frequencies of subjects with AFP levels <20, 20-200, or >200 ng/mL will be presented by treatment for each cycle.

Liver Chemistry Tests, INR, and viral load will be summarized using descriptive statistics and clinically significant abnormalities will be listed. Additionally, between-treatment comparisons with respect to these laboratory parameters will be performed using ANCOVA with the baseline value used as a covariate.

The relationship between WBC A₃AR expression and clinical response will be assessed by providing the counts and percentages for Overall Response by Change from Baseline (CFB) in A₃AR expression categorized as less than or at least the median by treatment at each visit.

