#### Table Format Specification

Maximum and minimum values will be reported with the same number of decimal places as collected. Means and medians will be reported to one additional decimal place. Standard deviations and standard errors will be reported to two decimal places more than the collected data. Percents will be reported with one decimal place. P-values will be rounded to three decimal places (e.g., "0.xxx"). If a p-value <0.001, then the p-value will be reported as "<0.001".

If the frequency is 0 or 1 for a category for calculation of a standard deviation or standard error, then enter '(NE)' for calculation of the standard deviation or standard error and add a footnote (penultimate preceding Source) of 'NE= Not Estimable'.

If the frequency for "Total" <2 for a categorical variable for either treatment group, or frequency is "Total" for any category, i.e. a percent of 100 for that category, for both treatment groups, then enter 'NA' for the p-value with a footnote (penultimate preceding "Source") of 'NA = Not Applicable'.

Data in the tables are formatted as follows:

- Text fields in the body of the tables and listings will be left-justified.
- All numeric values between -1 and 1 are outputted with zero to the left of the decimal point (e.g. 0.12, 0.3).
- Unless otherwise specified, percentage values are output with one digit to the right of the decimal point (e.g., 12.3, 4.5). Percentages that are > 0.0 and < 0.1 (not 0.0) are reported as "< 0.1".

- When no data are available for a table, an empty page with the title will be produced with suitable text. Example: THERE WERE NO SERIOUS ADVERSE EVENTS.

For many variables assessed at Pre-Study Visit, Baseline=Cycle 1 Day 1 (or Pre-Study if <= 3 days prior to Cycle 1 Day 1) or if value at Cycle 1 Day 1 is missing. These are variables are identified with a footnote indicating this.

Dates will be presented as recorded. All listings will include the Safety Population and will be sorted by site, subject, and cycle (if appropriate). Treatments are to be formatted as CF102 and Placebo in listings.

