Percentages are calculated using the number of subjects in the ITT Population for each treatment as the denominator.

P-values determined using the normal approximation to the binomial distribution using observed responses.

ITT= Intent-to-Treat

NA = Not Applicable

Source: Listing 16.2.6.3.1

Programming Notes: Continue for all cycles through Cycle 11.

Use same structure for Table 14.2.2.1.2 (PP Population) with PP instead of ITT in the two appropriate footnotes and the last footnote changed to "Source: Listings 16.2.6.3.1, 16.2.1.2".

Table 14.2.2.2.1

Best Overall Response
ITT Population

	CF102	Placebo
Best Overall Response, n (%)	(N=xx)	(N=xx)
CR	xx (xx.x)	xx (xx.x)
PR	xx (xx.x)	xx (xx.x)
SD	xx (xx.x)	xx (xx.x)
PD	xx (xx.x)	xx (xx.x)
Total	xx	xx
ORR	xx (xx.x)	xx (xx.x)
P-value	0.xxxx	
DCR	xx (xx.x)	xx (xx.x)
P-value	0.xxxx	

CR=Complete Response, PR =Partial Response, SD =Stable Disease, PD=Progressive Disease

ORR=Objective Response Rate= proportion of subjects who have response of CR or PR

DCR=Disease Control Rate= proportion of subjects who have response of CR. PR, or SD

Percentages are calculated using the number of subjects in the ITT Population for each treatment as the denominator.

P-values determined using the normal approximation to the binomial distribution using observed responses.

Best Overall Response is determined for the entire duration of the study and is counted once per subject, although it may occur more than once.

ITT= Intent-to-Treat

NA = Not Applicable Source: Listing 16.2.6.3.1

Programming Notes: Best Overall Response is determined for the entire duration of the study. Use same structure for Table 14.2.2.2.2 (PP Population) with PP instead of ITT in the two appropriate footnotes and the last footnote changed to "Source: Listings 16.2.6.3.1, 16.2.1.2".

Table 14.2.3.1 WBC A3AR expression ITT Population

		CF102	Placebo
Visit	Statistic	(N=xx)	(N=xx)
Baseline	n	XX	XX
	Mean (SD)	xxx.x (xxx.xx)	xxx.x (xxx.xx)
	Median	XXX.X	XXX.X
	Min, Max	XXX, XXX	XXX, XXX
Cycle 3 Day 1	n	XX	XX
	Mean (SD)	xxx.x (xxx.xx)	xxx.x (xxx.xx)
	Median	XXX.X	XXX.X
	Min, Max	XXX, XXX	XXX, XXX
CFB at Cycle 3 Day 1	n	XX	XX
	Mean (SD)	xxx.x (xxx.xx)	xxx.x (xxx.xx)
	Median	XXX.X	XXX.X
	Min, Max	XXX, XXX	XXX, XXX
Cycle 5 Day 1	n	XX	XX
	Mean (SD)	xxx.x (xxx.xx)	xxx.x (xxx.xx)
	Median	XXX.X	XXX.X
	Min, Max	XXX, XXX	XXX, XXX
CFB at Cycle 5 Day 1	n	XX	XX
	Mean (SD)	xxx.x (xxx.xx)	xxx.x (xxx.xx)
	Median	XXX.X	XXX.X
	Min, Max	XXX, XXX	XXX, XXX

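### ORR, DCR and best response are tested with an unpooled Wald z-test whose true two-sided level at 52 vs 26 exceeds 5% for common rates of about 3.7% to 96.3%, peaking at 8.6%

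*SAP*

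**What the plan says.** SAP 7.6.4 says of ORR: "The between-treatment comparison will be performed using the normal approximation to the binomial distribution (NAB) with unequal variances, as follows". It then writes out Z with p(1−p)/n computed separately for each arm, and a two-sided normal p-value without continuity correction. The same test is applied to DCR by cycle and to both best-overall-response proportions (CR or PR; CR, PR or SD).

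The variance form is deliberate. SAP 7.6 says: "Binary response variables will not be analyzed using SAS PROC FREQ, which uses equal variances for the differences". The protocol is less specific. Section 12.4.2 says only that "between-treatment comparisons will be performed using the normal approximation to the binomial distribution by treatment for each even-numbered cycle", so unequal variances is a choice made in the SAP.

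The Table Format Specification withholds a p-value if either arm's total is below 2, or if a single category holds every subject "for both treatment groups, then enter 'NA' for the p-value". Footnotes to Tables 14.2.2.1.1 and 14.2.2.2.1 say "Percentages are calculated using the number of subjects in the ITT Population for each treatment as the denominator" but also "P-values determined using the normal approximation to the binomial distribution using observed responses".

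**The concern.** In a small arm with few responders, the separately estimated variance is often far too small. With no responders on placebo it is exactly zero, and the standard error then comes from CF102 alone. The NA rule does not catch this case, because it needs an arm total below 2 or a degenerate result in both arms.

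ORR and DCR are named secondary endpoints and the tables will print their p-values. A reader who compares those with 0.05 may see a response difference in counts that exact tests do not support. At low rates most of the false positives would favour CF102.

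Separately, the two footnotes leave it open whether the n in each cycle's Z is the ITT number or the number assessed at that cycle.

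**Working it through.** **Inputs**

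- Statistic (SAP 7.6.4): Z = (pCF − p0) / √[pCF(1−pCF)/nCF + p0(1−p0)/n0], p = 2(1 − Φ(|Z|)).
- Arm sizes: 78 at 2:1 (Protocol 6.3) gives 78 × 2/3 = 52 and 26. SAP Section 9 says no subject was excluded from ITT; actual arm sizes are not given.
- Level: 5% two-sided is stated only for the logrank test (Protocol 12.2). Using it here is an assumption.
- Likely rates (Protocol 4.2.2): in the earlier phase 1/2 trial the best response was stable disease, in 5 of 17 (29.4%). That implies 0/17 with CR or PR, with an exact 95% upper limit of 1 − 0.025^(1/17) = 19.5%.
- Tables with no p-value count as no rejection.

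**The plan's own figure.** The only sample-size statement is 75 deaths for 80% power at a hazard ratio of 0.5. Schoenfeld's formula at 2:1 gives (1.960 + 0.842)² / [(2/3)(1/3)(ln 0.5)²] = 7.85/0.1068, or 74 deaths, and 80.8% power at 75. That figure reproduces. Nothing comparable is stated for response.

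**Exact level.** For a common true rate p, sum Bin(a; 52, p) × Bin(b; 26, p) over all 53 × 27 tables with |Z| > 1.96, with p from 0.001 to 0.999 in steps of 0.001.

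| Common rate | SAP test | Pooled z | Fisher |
|---|---|---|---|
| 1% | 0.15% | 1.6% | 0.1% |
| 2% | 1.3% | 3.4% | 0.6% |
| 3% | 3.4% | 4.1% | 1.1% |
| 3.7% | 5.0% | 4.1% | 1.5% |
| 5% | 7.4% | 4.0% | 2.0% |
| 7% | 8.6% | 4.1% | 2.6% |
| 10% | 7.5% | 4.6% | 3.0% |
| 29.4% | 6.3% | 4.9% | 3.6% |
| 50% | 6.6% | 4.6% | 3.1% |
| Maximum | 8.6% | 5.2% | 3.8% |

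The SAP level crosses 5% only at about 3.7% and 96.3% and stays above 5% between them.

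**Direction.** At a common rate of 5%, 6.9 of the 7.4 points favour CF102 and 0.5 favour placebo. At 29% the split is 3.9 to 2.4. At 50% it is even.

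**Worked examples**

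- 4/52 vs 0/26: pCF = 0.0769, SE = √(0.0769 × 0.9231/52 + 0) = 0.0370, Z = 2.08.
- 21/52 vs 5/26: difference 0.4038 − 0.1923 = 0.2115, SE = √(0.00463 + 0.00597) = 0.1030, Z = 2.05.

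| Method | 4/52 vs 0/26 | 21/52 vs 5/26 |
|---|---|---|
| SAP p | 0.037 | 0.040 |
| Fisher p | 0.295 | 0.077 |
| Barnard p, pooled statistic | 0.160 | 0.065 |
| Barnard p, unpooled statistic | 0.086 | 0.086 |
| Boschloo p | 0.253 | 0.062 |
| Miettinen-Nurminen 95% CI, points | −5.7 to 18.3 | −1.3 to 39.5 |

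For 5/52 vs 0/26 the exact tests disagree (Fisher 0.163, Barnard 0.114 and 0.049), so that table is not used as evidence.

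**How many tables.** At 52/26, 64 tables have SAP p < 0.05 and Fisher p > 0.05. Of these, 34 also exceed 0.05 on both Barnard versions. At common rates of 5%, 7%, 29.4% and 50% those 34 contribute 3.8, 3.3, 1.7 and 2.1 points of the SAP level.

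**Sensitivity to arm sizes**

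| Split | Maximum level | Rate at which level crosses 5% |
|---|---|---|
| 50/28 | 7.8% | 4.1% |
| 51/27 | 7.9% | 3.9% |
| 52/26 | 8.6% | 3.7% |
| 53/25 | 9.4% | 3.6% |
| 54/24 | 10.3% | 3.4% |
| 30/15 | 9.1% | 6.4% |
| 20/10 | 9.6% | 9.0% |

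The last two rows show what happens if n is the number assessed at a later cycle. Across the first five, the level at rates of 29% to 50% is 5.6% to 6.6%.

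**The case against.** The strongest reply is about weight. These are unadjusted secondary p-values in a Phase 2 trial with a survival primary endpoint. The plan gives them no alpha and no success rule, and the primary logrank test does not depend on them. All of that stands.

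The 8.6% maximum also needs a common rate near 7%, which the documents do not point to. ORR could lie below 3.7%, where the test is conservative. At the one rate the documents suggest, about 29% for DCR, the excess is 1.3 points, and the lean toward CF102 there is much weaker. This also stands. The lean is in any case not peculiar to the SAP test: with sparse events at 2:1, the pooled z-test leans toward placebo.

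The count of 34 depends on which exact tests are consulted. Boschloo's test falls below 0.05 for four of them (24 vs 6, 26 vs 7, 26 vs 19 and 28 vs 20 responders), leaving 30. That is correct, so 34 should be read as unsupported by Fisher and both Barnard versions only. Both worked examples remain above 0.05 on Boschloo.

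Fisher's test is itself conservative, so part of any gap between the two p-values comes from Fisher. True, but its level never exceeds nominal, which is what a companion to an anti-conservative test must offer.

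Finally, the PROC FREQ sentence may help stop a programmer substituting an equal-variance result, so it could be narrowed rather than deleted. Deleting it does no harm, because 7.6.4 still gives the formula in full.

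**Conclusion.** The concern holds. At 52 vs 26 and a nominal two-sided 5%, the SAP test exceeds its level for common rates from about 3.7% to 96.3%, by up to 3.6 points (8.6%), and by 1.2 to 1.6 points at rates of 29% to 50%. It is conservative outside that range. The excess comes from the unpooled variance rather than from normal approximation as such: the pooled form, which the protocol wording also allows, peaks at 5.2%.

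DCR is likely to fall in the inflated range; ORR may fall on either side of its lower limit. The result assumes the planned 2:1 split and a 5% level, and the nearby splits do not change it. It should be fixed before response results are interpreted, but it does not touch the primary analysis. The unclear per-cycle denominator is a separate and smaller gap.

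**What to change.** In SAP 7.6.4 and Tables 14.2.2.1.1 to 14.2.2.2.2:

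- Keep the pre-specified p-value. Beside it add Fisher's exact test, which needs no choice of statistic, and a Miettinen-Nurminen 95% confidence interval for the difference in proportions.
- Footnote that the normal-approximation p-value can exceed its nominal level at these sample sizes, and base no claim of a response difference on it alone.
- State the denominator used for each cycle's p-value.
- Remove the PROC FREQ restriction in SAP 7.6.
- Record the addition, and its timing relative to unblinding, in SAP Section 9.

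The cost is a few SAP lines, one footnote and some SAS options, with no new data. SAP version 7.0 already contains decisions taken after unblinding, so Fisher's test and the interval must be labelled as later additions. The existing test is not among the items noted as post-unblinding and keeps its pre-specified status. Because Fisher's true level is at most 3.8% at 52/26, some apparent differences will no longer be supported.
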